## ANNEX 4. CODES FOR COMORBIDITIES AND OTHER MEDICATIONS

Annex Table 4:1 Other comorbidity

| Disease Description   | ICD-10 Code   | ICD-9 Code  |
|---|---|---|
| Cardiovascular diseases  | I00-I99  | 390-459  |
| Ischaemic heart disease   | I20-I25 or coronary reperfusion surgery and procedures              | 410-414 or coronary reperfusion surgery and procedures              |
| Angina pectoris   | I20   | 413, 411.1  |
| Acute myocardial infarction   | I21   | 410   |
| Other acute or subacute ischaemic heart disease                         | I22-I24   | 411.0, 411.8  |
| Chronic ischaemic heart disease   | I25   | 412, 414  |
| Coronary reperfusion surgery and procedures                             | List of codes to be developed according to each database dictionary | List of codes to be developed according to each database dictionary |
| Arrhythmias   | I47-I49   | 427.0-427.4, 427.6-427.9  |
| Paroxysmal tachycardia  | I47   | 427.0-427.2   |
| Ventricular tachycardia   | I47.0, I47.2  | 427.1   |
| Supraventricular tachycardia and unspecified                            | I47.1, I47.9  | 427.0, 427.2  |
| Atrial fibrillation and flutter   | I48   | 427.3   |
| Other cardiac arrhythmias   | I49   | 427.4, 427.6, 427.8, 427.9  |
| Ventricular fibrillation and flutter                                    | I49.0   | 427.4   |
| Other cardiac arrhythmias   | I49.1-I49.9   | 427.6, 427.8, 427.9   |
| Conduction disorders  | I44-I45   | 426   |
| Cardiac arrest  | I46   | 427.5   |
| Heart failure   | I50   | 428   |
| Cerebrovascular disease   | I60-I69, G45  | 430-438   |
| Cerebral haemorrhage (subarachnoid, intracerebral, other non-traumatic) | I60-I62   | 430-432   |

Annex Table 4:1 (con't) Other comorbidity

| Disease Description  | ICD-10 Code  | ICD-9 Code   |
|---|---|---|
| Cardiovascular diseases  | I00-I99  | 390-459  |
| Cerebral infarction and stroke  | I63, I64, G46.5   | 433.1, 434.1, 436   |
| Transient ischaemic attack  | G45   | 435   |
| Other cerebrovascular disease and sequelae of cerebrovascular disease | I65-I69   | 433.0, 434.0, 437, 438  |
| Hypertension and hypertensive heart disease                           | I10-I15   | 401-405   |
| Diseases of arteries, arterioles, and capillaries                     | I70-I79, and peripheral arterial revascularisation procedures       | 440-449 and peripheral arterial revascularisation procedures        |
| Peripheral arterial revascularisation procedures                      | List of codes to be developed according to each database dictionary | List of codes to be developed according to each database dictionary |
| Other form of heart diseases  | I00-I09, I30-I43, I80-I99   | 390-398, 420-425, 429, 440-459                                      |
| Hyperlipidaemia  | E78  | 272  |
| Diabetes mellitus  | E10-E14  | 250  |
| Renal disease  | N00-N39  | 580-599  |
| Chronic kidney disease  | N18   | 585   |
| Other renal disorders   | N00-N17, N19, N25-N39   |   |
| Anaemias   | D50-D64  | 280-285  |
| Nutritional anaemias  | D50-D53   | 280-281   |
| Iron deficiency anaemias  | D50   | 280   |
| Other anaemias  | D55-D64   | 282-285   |
| Peptic ulcer disease   | K25-K28  | 531-534  |
| Liver disease  | K70-K77  | 570-573  |
| Osteoporosis   | M80-M82  | 733.0  |
| Rheumatoid arthritis and other inflammatory arthropathies      | M05-M14  | 712-714, 716, 696.0  |
| Systemic connective tissue diseases                            | M30-M36  | 710  |
| Malignancy   | C00-C97  | 140-209  |
| Depressive disorders   | F32-F33  | 311,   |
| Pregnancy (at the index date)                                  | O00-O48  | 630-649  |

ICD-10 = *International Statistical Classification of Diseases and Related Health Problems, 10th Revision*; ICD-9 = *International Classification of Diseases, 9th Revision*.

Annex Table 4:2 Anatomical Therapeutic Chemical codes for comedications

| Medication Description  | ATC Code |
|--------------------------------|-----------------|
| Respiratory medications |                 |
| Inhaled SAMAs                  |                 |
| Ipratropium bromide            | R03BB01         |
| Oxipropium bromide             | R03BB02         |
| Inhaled LAMAs                  |                 |
| Tiotropium bromide             | R03BB04         |
| Acclidinium bromide            | R03BB05         |
| Glycopyrronium bromide         | R03BB06         |
| Inhaled SABAs                  |                 |
| Salbutamol                     | R03AC02         |
| Terbutaline                    | R03AC03         |
| Fenoterol                      | R03AC04         |
| Rimiterol                      | R03AC05         |
| Hexoprenaline                  | R03AC06         |
| Isoetarine                     | R03AC07         |
| Pirbuterol                     | R03AC08         |
| Tretoquinol                    | R03AC09         |
| Carbuterol                     | R03AC10         |
| Tulobuterol                    | R03AC11         |
| Clenbuterol                    | R03AC14         |
| Reproterol                     | R03AC15         |
| Procaterol                     | R03AC16         |
| Bitolterol                     | R03AC17         |
| Indacaterol                    | R03AC18         |
| Inhaled LABAs                  |                 |
| Salmeterol                     | R03AC12         |
| Formoterol                     | R03AC13         |
| Inhaled glucocorticosteroid    |                 |
| Beclometasone                  | R03BA01         |
| Budesonide                     | R03BA02         |

Annex Table 4:2 (con't) Anatomical Therapeutic Chemical codes for comedications

| Medication Description                                    | ATC Code  |
|---|---|
| Respiratory medications                            |   |
| Flunisolide   | R03BA03   |
| Betamethasone   | R03BA04   |
| Fluticasone   | R03BA05   |
| Triamcinolone   | R03BA06   |
| Mometasone  | R03BA07   |
| Ciclesonide   | R03BA08   |
| Fixed combinations of SABAs and SAMAs                     | ATC codes not available                                     |
| Fixed combinations of SABAs and ICSs                      | ATC codes not available                                     |
| Fixed combinations of LABAs and ICSs                      | ATC codes not available                                     |
| Systemic glucocorticosteroids                             | H02AB   |
| Systemic beta2-agonists                                   | R03CC   |
| Xanthines and adrenergics                                 | R03DA, R03DB  |
| Roflumilast   | R03DX07   |
| Nasal glucocorticosteroids                                | R01AD   |
| Omalizumab  | R03DX05   |
| Leukotriene receptor antagonists                          | R03DC   |
| Cromoglicic acid  | R03BC01   |
| Nedocromil  | R03BC03   |
| Methotrexate  | L04AX03   |
| Ciclosporin   | L04AD01   |
| Gold preparations   | M01CB   |
| Oxygen therapy  | V03AN01   |
| Nebuliser therapy   | ATC codes not available                                     |
| Cardiovascular medications                         | All codes listed below in section
Cardiovascular medications |
| Cardiac glycosides and antiarrhythmics, Classes I and III | C01A, C01B  |
| Vasodilators used in cardiac diseases                     | C01D  |
| Other cardiac preparations                                | C01B, C01C  |
| Diuretics   | C03   |
| Peripheral vasodilators                                   | C04   |

Annex Table 4:2 (con't) Anatomical Therapeutic Chemical codes for comedICATIONS

| Medication Description   | ATC Code  |
|--|---|
| Cardiovascular medications  | All codes listed below in section Cardiovascular medications |
| Beta blocking agents   | C07   |
| Calcium channel blockers   | C08   |
| Antihypertensives  | C02   |
| Agents acting on the renin-angiotensin system  | C09   |
| Angiotensin-converting-enzyme inhibitors   | C09A, C09B  |
| Angiotensin II receptor antagonists  | C09C, C09D  |
| Renin-inhibitors   | C09X  |
| Lipid-modifying agents   | C10   |
| HMG CoA reductase inhibitors (statins)   | C10AA   |
| Other lipid-modifying agents   | C10AB, C10AC, C10AD, C10AX  |
| HMG CoA reductase inhibitors (statins), other combination  | C10BX   |
| Antithrombotic agents   | B01  |
| Platelet aggregation inhibitors  | B01AC   |
| Systemic antibacterials   | J01  |
| Iron preparations   | B03A   |
| Proton pump inhibitors  | A02BC  |
| Drugs used in diabetes  | A10  |
| Insulins   | A10A  |
| Blood glucose-lowering drugs   | A10B, A10X  |
| Drugs for musculoskeletal system  | M01A, N02BA, M01B, M01C                                      |
| Antiinflammatory and antirheumatic products, non-steroids (nonsteroidal anti-inflammatory drugs)                | M01A  |
| Acetylsalicylic acid (other analgesics and antipyretics)   | N02BA   |
| Other antirheumatic agents: Antiinflammatory/antirheumatic agents in combination, specific antirheumatic agents | M01B-M01C   |
| Antidepressants   | N06A   |
| Selective serotonin reuptake inhibitors  | N06AB   |
| Antineoplastic agents   | L01  |

Annex Table 4:2 (con't) Anatomical Therapeutic Chemical codes for comedICATIONS

| Medication Description   | ATC Code         |
|---|-------------------------|
| Immunosuppressants   | L04              |
| Antivirals for systemic use  | J05              |
| Hormone-replacement therapy: Estrogens, progestogens, and estrogens in combination | G03C, G03D, G03F |
| Drugs used in nicotine dependence  | N07BA            |

ATC = Anatomical Therapeutic Chemical; ICS = Inhaled Glucocorticosteroid; LABA = Long-Acting Beta2-Agonist; LAMA = Long-Acting Muscarinic Antagonist; SABA = Short-Acting Beta2-Agonist; SAMA = Short-Acting Muscarinic Antagonist.

1 The national drug code of each database country will be used to identify medications without an individual ATC code.

Source: WHO Collaborating Centre for Drug Statistics Methodology. ATC/DDD Index 2013. Updated 20 December 2012.

Available at: [website: whooc.no/atc\\_ddd\\_index/](http://www.whooc.no/atc_ddd_index/). Accessed 21 January 2013.

[figure not shown]
## ANNEX 5. DETAILS ON EACH DATABASE FROM THE FEASIBILITY REPORT (1 NOVEMBER 2013)

### PHARMO, THE NETHERLANDS

#### Database Characteristics

##### Database Description

[figure not shown]
The PHARMO Database Network consists of multiple databases containing data files on approximately 3.2 million community-dwelling inhabitants in geographically defined areas covering approximately 20% of the Netherlands. [Annex Figure 5:1](#) shows the databases included in the PHARMO Database Network. Data sources include information from GPs, community pharmacies, hospitals, and laboratory sources.

GP = General Practitioner; PRO = Patient-Reported Outcome.

#### Annex Figure 5:1 Data sources within the PHARMO Database Network

The patients covered in each database are not necessarily included in all of the databases, as some of the geographical areas overlap partially; but if patients are in more than one database, they can be linked to construct the medical history as shown in [Annex Figure 5:2](#). Thus, high-quality research has been conducted with ascertainment of patient demographics, drug dispensings, hospital morbidity, clinical laboratory results, and date of death.

GP = general practitioner.

Annex Figure 5:2 Schematic overview of overlap example among databases included in the PHARMO Database Network

2. LIST OF ABBREVIATIONS

Term	Definition / description
ATC	Anatomical Therapeutic Chemical
BI	Boehringer Ingelheim
BMI	Body Mass Index
CBV	Centraal Beheer Verrichtingenbestand (Dutch) [Central File Management Operations]
COPD	Chronic Obstructive Pulmonary Disease
DDD	Defined Daily Dose
EMA	European Medicines Agency
EphMRA	European Pharmaceutical Market Research Association
FEV1	Forced Expiratory Volume in 1 Second
GOLD	Global Initiative for Chronic Obstructive Lung Disease
GP	General Practitioner or General Practice
ICD	International Classification of Diseases
ICD-10	International Statistical Classification of Diseases and Related Health Problems, 10th Revision
ICD-9	International Classification of Diseases, 9th Revision
ICPC	International Classification of Primary Care
ICS	Inhaled Glucocorticosteroid
LABA	Long-Acting Beta2-Agonist
LAMA	Long-Acting Muscarinic Antagonist
LPD	Longitudinal Patient Database
NCSP	Nordic Medico-Statistical Committee Classification of Surgical Procedures
PASS	Postauthorisation Safety Study
PHARMO	Institute for Drug Outcomes Research (the Netherlands); also short for the PHARMO Database Network
PHARMO-GP	a data subset of PHARMO Database Network with information from GPs
RWE	Real-World Evidence
SABA	Short-Acting Beta2-Agonist
SAMA	Short-Acting Muscarinic Antagonist

Proprietary confidential information © 2017 Boehringer Ingelheim International GmbH or one or more of its affiliated companies

Term	Definition / description
WHO	World Health Organization

3. INTRODUCTION

This statistical epidemiologic analysis plan (SEAP) provides a description of the plan for conducting the analyses for a drug utilisation study, qualified as a postauthorisation safety study (PASS), for Striverdi® (olodaterol).

The study primary objectives are to (1) quantify the frequency of off-label use of olodaterol among new users of this medication and (2) describe recorded baseline characteristics of new users of olodaterol. The study secondary objectives are to (1) quantify the frequency of off-label use of indacaterol among new users of this medication and (2) describe recorded baseline characteristics of new users of indacaterol.

Both olodaterol and indacaterol are indicated for maintenance bronchodilator treatment of airflow obstruction in adult patients with chronic obstructive pulmonary disease (COPD) [[R16-2633](#), [R16-2634](#)]. The study will quantify frequency of off-label use in indications that are not COPD, e.g., asthma, and among populations not included in the label, e.g., children.

This is an observational cohort study using information collected in the following databases: (1) the PHARMO Database Network in the Netherlands (PHARMO), which includes the Out-patient Pharmacy Database, the General Practitioner (GP) Database, and the Hospitalisation Database; (2) the National Registers in Denmark, which are linkable through the centralised Civil Registration System and will include for this study the Danish National Patient Registry (inpatient hospital data and outpatient hospital clinic data) and the Danish National Health Services Prescription Database; and (3) the IMS Real-World Evidence (RWE) Longitudinal Patient Database (LPD) in France, an anonymised medical records database that includes a panel of 1,200 primary care physicians and a pulmonologist panel including 40 specialists. For additional details of the study data sources, see [Table 2](#) and [Table 3](#) in Section [5](#).

RTI Health Solutions serves as the coordinating centre and is responsible for leading development of the study protocol, SEAP, and study reports and for providing support and oversight to each of the research partners who will carry out the analysis within their own institutions.

The study period will start on the date of olodaterol launch in each country and will end on the latest date the data are available at the time of data extraction. Anticipated study periods for each data source at the time of data extraction and reporting milestones are shown in [Table 1](#).

Proprietary confidential information © 2017 Boehringer Ingelheim International GmbH or one or more of its affiliated companies

Table 1 Estimated study period in each study data source and reporting milestones

Event	PHARMO, the Netherlands	National Registries, Denmark	IMS RWE LPD, France
Olodaterol launch in country	March 2014	January 2014	October 2015
Data extraction for interim report	Q1 2017	Q1 2017	Q1 2017
Anticipated study period included in interim report ¹	March 2014 – Q4 2015	January 2014 – Q4 2015	October 2015 – Q4 2016
Interim report regulatory milestone	Q3 2017	Q3 2017	Q3 2017
Data extraction for final report	Q1 2018	Q1 2018	Q1 2018
Anticipated study period for final report	March 2014 – Q4 2016	January 2014 Q4 2016	October 2015 – Q4 2017
Final report regulatory milestone	Q3 2018	Q3 2018	Q3 2018

IMS = IMS Health Information Solutions; PHARMO = PHARMO Database Network; Q_n = the quarter of the calendar year; RWE LPD = Real-World Evidence Longitudinal Patient Database.

1. Study periods of observation are estimated based on the following lag times in each data source: PHARMO, approximately 6 to 18 months, Danish registries, approximately 6 to 12 months; IMS RWE LPD, 2 to 7 months.

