## 6. MILESTONES

| Milestone   | Planned Date                                 |
|--|---|
| Start of data collection (expected availability of data on earliest exposure group entry)  : | Denmark: Q1 2015
The Netherlands: Q4 2015
Sweden: Q4 2015 |
| End of data collection (latest possible exposure group entry):   | Denmark: Q1 2018
The Netherlands: Q1 2018
Sweden: Q1 2018 |
| Study progress report(s):  | TBD   |
| Interim report(s) of cumulative study results:   | Q3 2017   |
| Registration in the EU PAS register:   | After regulatory endorsement of the protocol                    |
| Final report of study results from all databases:  | Q3 2018   |

TBD = to be determined. Contact with database custodians is pending.

- 1 Preliminary; dependent on market uptake of olodaterol and contracts with MAH and research partners.
- 2 Considering launch dates and approximately 1-year lag time in database. Launch dates are March 2014 in Denmark, February 2014 in the Netherlands, and August 2014 in Sweden.

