### 9.2.2 Study period

The start of the study period is at the index date, defined as the dates of the first recorded dispensings of olodaterol and indacaterol in each database. New users of olodaterol and indacaterol will be identified in each of 3 consecutive years, with annual cross-sectional evaluations of off-label use and of characteristics of users.

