6.3 PATIENT SETS ANALYSED

Patients in the study will be required to meet the following criteria, as ascertained from each of the data sources:

- Receive a first dispensing for single-agent formulations of olodaterol or indacaterol during the study period with no prescriptions/dispensings ever before (see study period in [Table 1](#))
- Have at least 1 year of continuous enrolment in the data source immediately preceding the index date
- Have available data and no implausible values for age (< 0 years and > 120 years) or sex

Two study medication groups will be created: (1) a group of new users of olodaterol and (2) a group of new users of indacaterol. Inclusion in the study cohort as a new user in one of the two groups does not preclude the patient from being included as a new user in the other group if the inclusion criteria are met. The number of patients included in both groups will be reported.

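### SAP Table 1 and the protocol give conflicting olodaterol launch months for the Netherlands and Denmark, and the SAP uses launch to open the entry window for both drugs

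*SAP*

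**What the plan says.** SAP Section 3 sets the opening of the study period: "The study period will start on the date of olodaterol launch in each country". Table 1 in the same section has a row headed "Olodaterol launch in country", which gives March 2014 for PHARMO and January 2014 for Denmark. Its period rows start in the same months: "March 2014 – Q4 2015" (PHARMO, interim), "January 2014 – Q4 2015" (Denmark, interim) and "March 2014 – Q4 2016" (PHARMO, final). The final Danish period runs from January 2014 to Q4 2016.

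The period is an eligibility limit. SAP Section 5 takes as index date the first record of either drug inside the period and refers to Table 1. Sections 6.1 and 6.3 also refer to Table 1, and Section 6.3 requires a first dispensing "during the study period with no prescriptions/dispensings ever before".

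Protocol Section 6, footnote 2, reads: "Launch dates are March 2014 in Denmark, February 2014 in the Netherlands, and August 2014 in Sweden". Protocol Section 9.2.2 does not use a launch month. It opens the period at the index date, "defined as the dates of the first recorded dispensings of olodaterol and indacaterol in each database".

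**The concern.** A country has one launch date, so for each of these two countries at least one document is wrong. Both statements are current text, not a record of superseded wording.

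A wrong milestone month would normally be cosmetic. Here it matters because the month opens the entry window and the new-user rule looks back over all recorded history. If the window opens too late, patients who started before it are not picked up at their next dispensing; they are never eligible. If it opens too early, no olodaterol user is lost, but indacaterol starters are collected from weeks in which olodaterol could not have been chosen. Indacaterol is in the study to put the olodaterol result into perspective, and a shared calendar window serves that purpose best.

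The research centres work from both the protocol and the SAP (SAP Section 7), so they could also apply different start months.

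**Working it through.** The plan states no month count to reproduce. The check sets the dates side by side, applies the SAP's own rules and counts calendar months.

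**Inputs**

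| | Protocol Section 6, footnote 2 | SAP Table 1 | SAP minus protocol |
|---|---|---|---|
| Netherlands | February 2014 | March 2014 | 1 month later |
| Denmark | March 2014 | January 2014 | 2 months earlier |

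For both countries the period ends in Q4 2015 (interim) and Q4 2016 (final), taken as December.

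**Formula.** Inclusive months = 12 × (end year − start year) + (end month − start month) + 1.

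**Final report, to December 2016**
- Netherlands, SAP start: 24 + (12 − 3) + 1 = 34. Protocol launch month: 24 + (12 − 2) + 1 = 35. Difference 1 month; 1/35 = 2.9%.
- Denmark, SAP start: 24 + (12 − 1) + 1 = 36. Protocol launch month: 24 + (12 − 3) + 1 = 34. Difference 2 months; 2/36 = 5.6%.

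**Interim report, to December 2015**
- Netherlands: 22 months against 23; 1/23 = 4.3%.
- Denmark: 24 months against 22; 2/24 = 8.3%.

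**2014 alone.** SAP Section 7.1.1 reports new-user counts, age and sex by calendar year, so any effect falls in the 2014 column: 1 of the 11 Dutch months from February to December (9.1%), and 2 of 12 Danish months (16.7%).

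**What the rules do if the protocol months are true and Table 1 is applied as printed**
- *Netherlands.* A patient first dispensed olodaterol in February 2014 has that dispensing before the window. A refill in March or later is inside it but fails the requirement of no previous dispensing, so the patient never enters. Dutch indacaterol starters of February are left out in the same way.
- *Denmark.* Indacaterol starters of January and February 2014 meet every criterion and enter. No olodaterol could yet be dispensed, so the olodaterol group loses nobody.

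**What the rules do if the SAP months are true.** Neither effect occurs.

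**The case against.** The strongest reply is that the SAP's rule is tied to an event. The period opens at launch, Table 1 is titled as an estimate, and its period rows are labelled anticipated. If the Dutch launch was in February, the sentence in Section 3 itself opens the window in February. That stands in part: the loss needs the printed month to be used as a cut-off. But Sections 5, 6.1 and 6.3 all refer to Table 1 for the period, and the table's footnote explains the estimates by data lag, which bears on the end of a period and not on the launch month. The ambiguity remains.

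The protocol dates may also be the wrong ones. Its abstract says olodaterol had not reached the European market, the milestones are marked preliminary, and the SAP is from 2017. Against that, the protocol's milestones were updated on 30 September 2014, after every launch month it lists, and the footnote is worded as fact. The documents leave this open.

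A reader might infer more than the documents support:
- *That Dutch first-month users will be lost.* This is conditional on both points above. One month in 35 is calendar time, not patients, because no monthly uptake is given.
- *That the earliest users matter most for off-label use.* Neither document says so; the objectives concern all new users.
- *That the SAP changed the start rule without declaring it.* Section 4 lists no such change, but it is also silent on replacing Sweden with France. A later protocol version that was not supplied may explain both.
- *That the mismatch costs the study its three consecutive years.* The SAP's own dates already give 34 months in the Netherlands and 27 in France (October 2015 to December 2017: 24 + 2 + 1).
- *That the protocol's start rule is better throughout.* It protects olodaterol users, but its wording also covers first recorded indacaterol dispensings, and protocol Table 8 shows indacaterol use from 2010. The SAP's common start is better for concurrency.

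Some mitigation is planned. The attrition table in SAP Section 7 would probably show patients removed because they started before the window.

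**Conclusion.** The contradiction is real and affects a date that decides eligibility; its consequences are conditional and small. At most, 1 of 35 Dutch calendar months of olodaterol entry is lost and 2 of 36 Danish months of indacaterol entry are not concurrent, both in the final report. This requires the protocol's launch months to be the true ones and Table 1 to be applied as a cut-off. The Danish effect touches only a descriptive secondary outcome, with no formal comparison planned. That few patients are affected is an assumption about low early uptake, not a derived figure. This is a minor correction, worth making because it is almost free and is safe whichever launch months are right.

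**What to change.** 1. Reconcile the launch months for the Netherlands and Denmark between protocol Section 6 and SAP Table 1.
2. In SAP Section 3 and Table 1, start each database's study period at the first recorded dispensing or prescription of single-agent olodaterol (R03AC19) in that database, whether or not that patient proves eligible.
3. Use the same date to open indacaterol entry.
4. Report the observed date for each database in place of the launch month.

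With this rule the start date cannot exclude an olodaterol user, and the indacaterol group cannot begin before olodaterol is in use in that database. The cost is one sentence and one table row in the SAP. The date comes from the planned extract, so no new data are needed.
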